6. Subjects in PTSD-focused psychotherapy may be enrolled if they have been in therapy for 6 weeks prior to randomization.
7. Able to provide written informed consent.
8. Able to read and write English.

Exclusion Criteria:

1. Subjects with a diagnostic history of schizophrenia or schizoaffective disorder as confirmed by the Mini-International Neuropsychiatric Interview (MINI) 7.0 for DSM-V.
2. Subjects with a history of antidepressant-induced hypomania or mania.
3. Subjects currently exhibiting psychotic features or meeting criteria for current manic, hypomanic, or mixed episode as confirmed by the MINI 7.0 for DSM-5.
4. Current, ongoing serious suicidal risk as assessed by evaluating investigator.
5. Moderate severity or greater Substance Use Disorder (excepting Alcohol Use Disorder) during the 3 months prior to randomization, as determined by the MINI 7.0 for DSM-5. Alcohol Use Disorder may be allowed based on the judgment of study physician/APRN/clinician that patients can remain sober for all study visits.
6. Subjects on a prohibited medication (see Table 1). Patients will not be taken off medication for the purpose of this study.
7. Any history or signs of serious medical or neurological illness. A subject with a clinical abnormality may be included only if the study clinician considers the abnormality will not introduce additional risk factors and will not interfere with the study procedure.
8. History of traumatic brain injury (TBI) with loss of consciousness for more than 24 hours or posttraumatic amnesia for more than 7 days may be considered if the trauma occurred more than 1 year ago, and no more than minimal symptoms have persisted over the past year.
9. Breathalyzer showing an alcohol level > 0% at screening, or at the discretion of the investigator, prior to any study drug infusion.
10. Any history indicating dementia or mental retardation as determined by psychiatric interview.
11. Known sensitivity to ketamine as determined by the study clinician.
12. At screening, resting blood pressure (sitting or supine) lower than 90/60 or higher than 150/90, or resting heart rate lower than 45/min or higher than 100/min.

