Criteria for Discontinuation: Subjects may be discontinued from study treatment and assessments at any time. Specific reasons for discontinuing a subject from this study are:

- Voluntary discontinuation by the subject, who is at any time free to discontinue his/her participation in the study without prejudice to further treatment.
- Clinical deterioration: The following are objective criteria to trigger full assessment, by the study investigator, for possible discontinuation at the investigator discretion: (a) A 25% increase in the PCL-5 or the CAPS-5 score at any time during the study; (b) Patients with a CGI score ≥ 6 at any post-baseline visit; or (c) the onset of active suicidality as assessed by the study clinicians or by scoring 5 or more on the item-10 of the MADRS.
- Evidence of intolerable adverse reaction, or unable to tolerate study drug.
- Safety reasons as judged by the investigator.
- Stopping birth control or a positive pregnancy test.
- Evidence of problematic alcohol use during the trial.
- Non-compliance to protocol procedures as judged by the investigator.

A subject who discontinues will always be asked about the reason(s) for discontinuation and the presence of any adverse events. If possible, they will be seen and assessed by a study investigator. Adverse events will be followed up as medically necessary.

Data Storage: Paper source documents and research case books will be housed in restricted access files. Personally-identified and protected information (PHI) will be restricted to name, address, phone number, birth-date, social security numbers, dates of care, and will be kept by investigators in a separate file from the research data which will be coded using a subject number assigned by the CAP Data Management and Biostatistics Core at the time of randomization.

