Delays in starting other treatments and the unproven therapeutic efficacy of study medication in this patient population may mean that subjects' conditions could worsen and lead to increased disturbances in mood, sleep, appetite, and cognition. This could result in loss of work and loss of social functioning. The most serious possible risk is the development of suicidal thoughts and/or behavior, if a subject's condition worsens. Subjects will be closely monitored for suicidality. Pertinent information regarding potential harm, including suicidality, homicidal intent, and ongoing elder or child abuse will be shared as necessary and required by law with clinicians and/or the appropriate authorities. In such circumstances, records may be made available to authorities, even without the subject's consent. Risks should be minimized as there are several safety precautions in place and subjects will remain in close contact with study clinicians.

As previously discussed, females of childbearing potential will likely be enrolled and safeguards

will be instituted (i.e. pregnancy test at screening, prior to each infusion, and requisite use of medically acceptable birth control method), to prevent pregnant subjects from enrolling or subjects conceiving during this investigation.

To control for the potential impact of the therapeutic milieu inherent to an inpatient unit, coupled with the recognition that mandatory inpatient admission would seriously threaten feasibility of recruitment, we propose to conduct the study on an outpatient basis. We believe our stringent selection procedures for study participants (which exclude psychosis, mania, substance use disorder, and active suicidality), as well as our close monitoring throughout the study, enable a safely conducted outpatient study. Additionally, inpatient admission is available to all subjects, if it is clinically indicated.

Research Risk

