Study infusion will be done in a medical setting, with continuous monitoring of respiratory and cardiac function (i.e., vital signs) will be done. Crash carts are available on the unit with medical personnel for immediate availability of resuscitative drugs and equipment in the event of an unexpected adverse drug reaction. Safety measures also include possible discontinuation of the study drug and transition to standard clinical treatment, should subjects worsen to a sufficient degree. In case of a medical emergency, the medication group blinding can be broken by the principal investigator, designated covering staff member or the research pharmacist, in order to supply information required for emergency medical care of research subjects. All subjects will be given a "wallet card" which identifies them as a study participant and lists the emergency contact numbers. If a subject shows clinical deterioration (worsening of PTSD symptoms), the study physician/APRN will determine whether: 1) the subject can remain in the study, or; 2) a higher level of care (e.g. referral back to treating psychiatrist or referral to emergency or inpatient care) is needed.

b. ***Suicidal Ideation and Imminent Harm:*** Office visits occur 1-2 times per week (i.e., infusions and follow-up visits as appropriate per protocol) throughout the treatment part of the clinical trial including phone calls during any week with missed study visits, to help ensure subject safety and protocol adherence. Study clinicians and raters ask patients about any new symptoms experienced at every visit and will assess subjects at each visit for suicide risk and potential. All communications about suicide and threats are taken seriously. Individuals at such risk will be treated appropriately, including options such as increased contact, more frequent clinical visits, or emergent psychiatric hospitalization. Subjects who score > 5 on the MADRS item 10 (suicide) at screening will be excluded from the study. In addition, an inability to control suicide attempts, imminent risk of suicide in the investigator's judgment, or a history of serious suicidal behavior. Throughout the study, any subject who presents with increased suicidality will be fully assessed for discontinuation (see above for discontinuation criteria). The study clinicians also reserve the right to complete the SITBI and DSS-IS at any point throughout the study if there are concerns

about a subject's suicidal ideations.

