All clinical staff associated with ratings have experience in psychiatric assessment and will implement protocol procedures in a sensitive and supportive manner. Interviews will be stopped if subjects become distressed or object to answering questions. In summary, measures to minimize risks include:

- Before participating, subjects undergo careful psychiatric and medical evaluation.
- An experienced research nurse and study clinician are available at all times during the infusion sessions to provide medical monitoring, support and consistent “reality testing” for individuals experiencing confusion or transient psychosis. Subjects will be debriefed; a review of the test day will be done with subjects to evaluate emotional response and to monitor adverse reactions to before they leave.
- If a subject reports that symptoms cannot be tolerated, the study drug infusion will be stopped.
- Subjects will be observed for 2 hours after the start of the infusion, and if intolerable physical or behavioral symptoms persist, they will be discontinued from the study. Subjects will then be treated as clinically indicated.
- Subjects will be informed that they may not drive or operate machinery for 12 hours after the end of test day procedures, and study staff will ensure that they are picked up by a responsible adult or safely reach their home on alternate transportation. They will also be advised to not engage in demanding work in the day following the test sessions. We will work with subjects to schedule the test days accordingly.
- Subjects will be provided a number to call to reach an on-call research psychiatrist (available 24 hours/day) should unpleasant effects occur after subjects have left the testing facility. They will also be provided with wallet cards identifying their participation in this study, should the research pharmacist need to break the study blind.
- If necessary, subjects will be administered IV lorazepam to reduce residual symptoms and their participation in the study will be terminated. Such subjects will be monitored as found appropriate by the study clinicians.
- In an effort to minimize risks, subjects with active suicidal ideation or recent self-injurious behavior will be excluded. During treatment phase, all subjects will be scheduled at our research clinic at a minimum of once to twice per week visits for ongoing assessment of behavioral symptoms as per protocol (e.g., infusion visits and follow-ups as appropriate).

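### The MADRS item 10 screening cut-off (> 5) lets through a score of exactly 5, which the discontinuation criteria count as active suicidality

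*Protocol*

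**What the plan says.** Five places in the protocol bear on this point. The SAP does not address eligibility.

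- **Section V, Protection against Risks to Subject Safety, item b (Suicidal Ideation and Imminent Harm).** The numeric entry rule is "Subjects who score > 5 on the MADRS item 10 (suicide) at screening will be excluded from the study". The next sentence adds grounds without a score: inability to control suicide attempts, imminent risk as judged by the investigator, and past serious suicidal behavior. The item later says that "any subject who presents with increased suicidality will be fully assessed for discontinuation".
- **Section IV.F, Criteria for Discontinuation.** Under clinical deterioration the protocol lists "objective criteria to trigger full assessment, by the study investigator, for possible discontinuation at the investigator discretion". Criterion (c) is "the onset of active suicidality as assessed by the study clinicians or by scoring 5 or more on the item-10 of the MADRS".
- **Section IV.B, exclusion criterion 4.** This reads "Current, ongoing serious suicidal risk as assessed by evaluating investigator", with no score attached.
- **Section V, Therapeutic Risks.** The case for running the study with outpatients rests in part on "stringent selection procedures for study participants (which exclude psychosis, mania, substance use disorder, and active suicidality").
- **Section V, list of measures to minimize risk.** Here "subjects with active suicidal ideation or recent self-injurious behavior will be excluded".

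Table 2 schedules item 10 alone at Visit 1 and the full MADRS for the first time at Visit 2 (Day 0, before the infusion). The DSI-SS and the SITBI are both marked at Visit 1. The Screening paragraph under Test Days places randomization after screening is complete.

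**The concern.** An entry threshold should be at least as strict as the on-study threshold for the same state on the same item. Here it is looser. Someone can be numerically eligible with a score that, once enrolled, calls for a full assessment with a view to discontinuation. The protocol gives no reason for the difference, and its stated intent points the other way, since the exclusion of active suicidality is offered as part of why an outpatient design is safe.

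What is at stake is participant safety at the point of entry, in a trial that names suicidal thoughts or behavior as its most serious possible risk and assigns one third of participants to placebo. There is a smaller operational cost as well: a person who could have been screened out may instead be randomized and then assessed or withdrawn before any dose. Because all analyses are intent-to-treat, that person would remain in the randomized population.

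**Working it through.** No design figure needs to be reproduced. The check compares two rules on one item and then follows the visit schedule.

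**Step 1. Compare the rules by score.** The screening rule is score > 5 (section V, item b). The on-study rule is score ≥ 5 (section IV.F, criterion c).

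| Item 10 score | Screening: excluded by the number? | On study: meets criterion (c)? | Agree? |
|---|---|---|---|
| Below 5 | No | No | Yes |
| Exactly 5 | No | Yes | **No** |
| Above 5 | Yes | Yes | Yes |

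The disagreement is confined to a score of exactly 5. The documents do not give the range or anchors of item 10, so nothing is inferred here about how many scores lie above 5.

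**Step 2. Look for another cut-off that resolves it.** Exclusion criterion 4 has no number. The two section V statements that active suicidality or active suicidal ideation is excluded have none either. The DSI-SS and SITBI are given at Visit 1, but neither has a stated cut-off. The numeric screening rule therefore stands alone, and the only other number for the same construct is the 5 or more in criterion (c).

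**Step 3. Follow a person who scores 5 at Visit 1.**

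1. Before randomization there is one item 10 rating (Visit 1). The numeric rule does not exclude.
2. Clinical judgment applies. It may exclude under criterion 4, under the sentence following the numeric rule, or under the list of risk-minimizing measures.
3. If not excluded, the person is randomized.
4. Between randomization and the first dose there is one full MADRS (Visit 2, Day 0, pre-infusion). Criterion (b) is "Patients with a CGI score ≥ 6 at any post-baseline visit"; criterion (c) carries no such limit. On that wording a 5 on Day 0 triggers a full assessment before dosing. The reading rests on the absence of a limit, and the word onset in criterion (c) leaves the investigator room to compare with the entry score.

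**Step 4. Size against the planned attrition.** From section IV.A:

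- Overall: 198 randomized − 159 completers = 39 non-completers allowed.
- Per group: 66 − 53 = 13.

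Each pre-dose withdrawal of this kind would be 1 of those 39. How many people would score exactly 5 cannot be derived from the documents.

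**The case against.** The strongest reply is that the two numbers do different jobs. The screening rule is an automatic exclusion, whereas criterion (c) sits under clinical deterioration, speaks of onset, and only triggers a review whose outcome is discretionary. A lower bar for a review and a higher one for automatic exclusion can be a coherent arrangement. On this view the mismatch appears only if the on-study marker is carried back to entry.

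A second reply is that nothing directs the enrollment of an actively suicidal person. If a 5 counts as active suicidality, the risk-minimizing list already requires exclusion. If it does not, the numeric rule contradicts nothing. Several clinical checks also stand between a score of 5 and randomization.

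A third is that the fix overreaches: criterion 4 was left to the evaluating investigator, and stating that criterion (c) means worsening from entry would also reconcile the text.

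Much of this stands as a limit on weight. The review is discretionary, clinical exclusion remains available, and the practical risk is small. It does not remove the inconsistency. The protocol chose to put a number on entry, that number is looser than its only other number for the same construct, and no reason is given. If a 5 must be excluded under the general wording, the numeric rule should say so. Redefining criterion (c) as change from entry would tidy the text but leave the looser entry rule in place. As for criterion 4, the protocol already contains a hard score exclusion in section V; the eligibility list simply omits it.

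**Conclusion.** The concern holds as an inconsistency in a safety threshold, limited to one score value. At exactly 5 on MADRS item 10, the numeric screening rule fails to exclude someone whom the protocol's own numeric marker would identify as actively suicidal. The documents do not say that such a person must be enrolled, because exclusion on clinical assessment remains open.

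The consequence is modest: mainly an avoidable assessment or withdrawal after randomization and before the first dose. That in turn assumes that criterion (c) applies on Day 0, as its wording allows. Sample size, power and analysis are not affected. The change should be made because the inconsistency concerns safety at entry and is cheap to remove; it does not threaten the trial's conclusions.

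**What to change.** Make two wording changes.

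1. In section V, Protection against Risks to Subject Safety, item b, replace the strict inequality so that a MADRS item 10 score of 5 or more at screening excludes. This matches criterion (c) in Criteria for Discontinuation.
2. In section IV.B, extend exclusion criterion 4 so that it is met either by the investigator's judgment of serious suicidal risk or by a MADRS item 10 score of 5 or more at screening. The judgment-based ground is kept, and the numeric rule then appears where staff look for eligibility.

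No assessment is added, since Table 2 already has item 10 at Visit 1. The cost is the two edits and possibly a few fewer eligible participants.

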SAFTEE	X	X	X	X	X	X	X	X	X	X
VR-12	X		X			X		X	X	X
WHYMPI	X		X			X		X	X	X
Cogstate	X		X			X		X		X
Physical Exam	X									
Medical History	X									
Routine Lab Tests	X									
Breathalyzer	X	X (PRE INF)	X	X (PRE INF)	X (PRE INF)	X	X (PRE INF)	X	X	X
ECG	X									
Serum Pregnancy Test	X									
Urine Pregnancy Test		X (PRE INF)		X (PRE INF)	X (PRE INF)		X (PRE INF)			
Blood Collection/Banking (e.g., DNA, RNA, Plasma, Serum)		X	X		X	X				X
Vital Signs	X	X (PRE,10, 20, 40)	X	X (PRE,10, 20, 40)	X (PRE,10, 20, 40)	X	X (PRE,10, 20, 40)	X	X	X
Infusion		X		X	X					
Open-Label Infusion							X			
IE Blinding Form						X				
Blinding Form						X				

*No study procedures will be completed prior to completion of the Informed Consent. The "Day" number is an approximation and the actual day may vary depending on delays in prior visits.

Test Days

Screening

Informed consent, physical examination and health assessment, ECG, laboratory tests, concomitant medications, MINI psychiatric assessment, and demographic information.

- Measures including, but not limited to, the DVBIC Brief TBI Screen, CAPS-5, PCL-5, MADRS (item 10 only), QIDS-SR, ARAC, CGI, PHQ-9, GAD-7, AUDIT, ISI, PROMIS Sleep, WHYMPI, Pain-NRS, VR-12, Cogstate, QDS will be administered. Refer to Table 2 for the full battery of measures and administration intervals.
- No more than 200 mL of blood will be collected for routine laboratory tests.
- After completing the screening and being deemed eligible for participation in the study, subjects will be randomized.

Infusion session 1 (Day 0)

- Infusions will take place at Biostudies, nursing/medical coverage will be provided by [name] [name] group, and will follow all related hospital and Biostudies standard operating procedures and policies.
- Breath alcohol, and urine pregnancy test;
- Blood collection for the biomarkers banking.
- AE Assessment since last visit;
- Intravenous lines started; Vital signs;
- Measures including, but not limited to, the PCL-5, MADRS, QIDS-SR, ARAC, CGI, GAD-7, PHQ-9, QDS, ISI, and will be completed prior to the study drug administration (refer to Table 2).
- Study drug will be infused over 40 minutes.
- Vital signs will be recorded at approximately 10, 20, and 40 minutes during infusion unless closer monitoring is clinically indicated.
- ARAC, CADSS and PANSS will be completed at 30 and 120 min following the start of the study drug infusion.

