- Subjects will be observed for at least 2-hours post start of the infusion and may be discharged after being cleared by a study physician/APRN. If intolerable physical or behavioral symptoms persist, they may be admitted to an inpatient unit for further observation and stay overnight if necessary. Subjects will then be discharged with appropriate follow-up care when his or her proximal safety risk is minimal.

Participants will be informed that they may not drive or operate machinery for 12 hours after the end of infusion day procedures, and study staff will ensure that they are picked up by a responsible adult or safely reach their home using alternate transportation.

Follow-up After First Infusion (Day 1)

- A follow-up session will be performed on Day #1. Assessment measures including, but not limited to, the PCL-5, ARAC, MADRS, QIDS-SR, GAD-7, CGI, ISI, QDS, Cogstate, and SAFTEE will be administered (refer to table 2).

- If subjects are unable to make this appointment, they will be contacted by phone 24 hours following study medication dosing, to assess side effects and stability of mood (PCL-5 & QIDS)

Infusion sessions 2-8 (Day 3, 7, 10, 14, 17, 21, 24)

- The protocol will be identical to the first session.
- Procedures for the twice per week infusions will follow the models presented above for the remaining 7 infusion sessions of the study, through Day-24.
- The twice weekly infusions will be scheduled to occur at least 48 hours apart.
- Blood for biomarkers will be collected on Day 14.

Follow-up after infusion session 8 (Days 25, 28, 35, 42, 49, 56)

- Clinical outcomes as detailed in Table 2 will be administered on these follow-up days.
- Blood for biomarkers will be collected on Days 25 and 56
- Following completion of the 4-week follow-up period, study clinicians will continue providing psychiatric care as needed until appropriate referral is arranged.

Open Label Infusion and Follow-up

- Non-responders (i.e., those with less than 25% improvement from the baseline CAPS-5 score) at the end of the double-blind treatment period (end of week 4) will be offered a single infusion of open-label ketamine (0.5 mg/kg). The infusion session procedures will be identical to those noted above. A 24-hour follow-up will also be conducted; the procedures will be identical to the follow-up procedures described above (Refer to Table 2).

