- If a subject's clinical condition significantly worsens, he or she will be discharged from the research protocol and referred for treatment in the most clinically appropriate setting.
- Study participants will be informed that a decision to initiate standardized psychotropic and/or psychotherapeutic regimens will not adversely affect their ability to participate in future protocols or receive treatment at any VA facilities.
- Subjects will continue to be followed weekly for 4 weeks following the last study infusion day. During these follow-up visits, patients will be evaluated for adverse events and complete psychiatric and medical symptom rating scales. Following completion of this 4-week follow-up period, study clinicians will continue providing psychiatric care as needed until appropriate referral is arranged.

These precautions are likely to be highly effective in minimizing risks. If a subject discontinues study medication, he/she will receive standard clinical treatment as indicated. If treatment is terminated due to adverse events or physical risks, subjects will be followed carefully until resolution of symptoms and treated with follow-up care as clinically indicated.

Possible Benefits:

Subjects may not receive any benefit from participating, although their participation may help patients in the future by giving important information about the study medication and PTSD. Subjects may benefit from initial screening procedures that will include a careful examination of their medical and psychiatric conditions. In the event that clinical abnormalities are discovered, subjects will be informed of the findings and referred for appropriate care.

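### Several safety rules end study participation rather than only infusions, and no PCL-5 or CAPS-5 is scheduled afterwards; the likely bias is small and the fix is cheap

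*Protocol*

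**What the plan says.** Three rules in the bulleted summary under Protection against Risks to Subject Safety end participation:

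- Intolerable symptoms at the two-hour check: "if intolerable physical or behavioral symptoms persist, they will be discontinued from the study".
- Rescue medication: "subjects will be administered IV lorazepam to reduce residual symptoms and their participation in the study will be terminated".
- Significant clinical worsening: "he or she will be discharged from the research protocol and referred for treatment in the most clinically appropriate setting".

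The Criteria for Discontinuation open with "Subjects may be discontinued from study treatment and assessments at any time" and list clinical deterioration and intolerable adverse reactions among the reasons. After a stop they require the reason and adverse events, and an investigator assessment where possible. No rating scale is named.

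Other text is softer:

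- For deterioration, the Criteria for Discontinuation set triggers for a full assessment and leave the decision to the investigator. The ketamine paragraph of the safety section, and section IV.C, also let the clinician decide whether the subject stays.
- For the two-hour event, the Infusion session 1 text says: "If intolerable physical or behavioral symptoms persist, they may be admitted to an inpatient unit for further observation and stay overnight if necessary". It then gives discharge with follow-up care and does not mention removal.
- The safety summary adds: "Subjects will continue to be followed weekly for 4 weeks following the last study infusion day". These visits include symptom rating scales.

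Table 2 has no early-termination visit. CAPS-5 is placed at screening, Day 25 and Day 56. PCL-5 is taken at each numbered visit and, on infusion days, before the drug is given.

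The Analysis plan makes all analyses intent-to-treat. The primary model is a mixed model valid under missing at random, with change from baseline to end-point of main interest. Pattern-mixture models follow only if dropout is disproportionate or missing at random is in doubt. The SAP's Supplemental section fits all available observations and counts missing data as failure for responder status.

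**The concern.** An intent-to-treat comparison needs end-point scores from people who stop treatment as well as from those who continue. Where a safety rule ends participation, those scores are not collected. A subject removed at infusion 1 has no post-treatment PCL-5 at all.

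The mixed model then fills the gap by assumption. For someone removed for a drug effect, missing at random implies an end-point like that of similar subjects in the same arm who carried on with infusions. If benefit fades once infusions stop, the model estimates something more favourable than the effect of being assigned to that arm.

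The direction follows from the Protocol's own statement, in the ketamine paragraph of the safety section, that acute symptoms become more common at higher doses. Tolerability removals would tend to fall in the 0.5 mg/kg arm and so flatter it against placebo and against 0.2 mg/kg.

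The inconsistent wording is a second problem. The same event two hours after an infusion starts leads to observation in one section and removal in another, so the two sites could act differently.

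**Working it through.** **Which rules are uncontradicted**

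| Trigger | Safety summary | Elsewhere in the Protocol |
|---|---|---|
| Intolerable symptoms at 2 hours | Removal from the study | Observation or admission, then follow-up care (Infusion session 1); listed as a permitted reason (Criteria for Discontinuation) |
| IV lorazepam | Participation ends | No softer version |
| Significant worsening | Discharge from the protocol | Clinician decides (Criteria for Discontinuation; ketamine safety paragraph; section IV.C) |

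The weekly follow-up bullet is not limited to completers, so it may cover some early stoppers. It does not naturally cover someone whose participation has been ended.

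**The plan's own figures**

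- Loss: 66 randomized and 53 completing per arm gives 1 − 53/66 = 19.7%, or 13 per arm. This is all-cause; the documents do not say how many would come from these rules.
- Pairwise power: with 53 per arm, d = 0.6 and two-sided alpha 0.025 (the second Holm step), the normal approximation gives 0.802. The stated 80% is reproduced.
- Planned effect of 0.5 mg/kg against placebo: d of at least 0.8 (Sample size justification).

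**Size of the overstatement**

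Assume that k of 66 in the 0.5 mg/kg arm are removed at infusion 1, that none are removed on placebo, that removal is unrelated to baseline, and that stoppers keep a fraction *h* of the benefit. Under missing at random the model returns d = 0.80, as if all had continued. The effect of assignment is

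0.80 × [1 − (k/66)(1 − h)],

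and the overstatement is 0.80 divided by that, minus 1.

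| k of 66 | None kept (h = 0) | Half kept (h = 0.5) |
|---|---|---|
| 1 | 0.788 (1.5%) | 0.794 (0.8%) |
| 3 | 0.764 (4.8%) | 0.782 (2.3%) |
| 8 | 0.703 (13.8%) | 0.752 (6.5%) |

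For k = 3 and h = 0: 0.80 × (1 − 3/66) = 0.764, and 0.80/0.764 − 1 = 4.8%.

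**Where k might lie**

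The documents give no rate. The nearest figure is one exit for discomfort during infusion among 41 patients in the single-infusion PTSD pilot (Background): 1/41 = 2.4%, exact 95% interval 0.1% to 12.9%. Applied to 66, that is 1.6 subjects, with an upper limit of 8.5. It is a loose guide only, because that exit was the subject's own choice and this trial gives eight infusions. The row for k = 8 is therefore a limit, not an expectation.

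**Against sampling error**

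The standard error of d at 66 per arm is √(2/66 + 0.80²/(4 × 66)) = 0.18. Three stops with no benefit kept shift d by 0.80 − 0.764 = 0.036, about 0.2 of a standard error.

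**The case against.** The strongest reply is that the removal bullets are a summary of safety measures, while the section devoted to discontinuation covers the same events and, for deterioration, leaves the decision to the investigator. A reader might infer from the bullets that the Protocol uniformly mandates removal for all three triggers. It does not, and only the lorazepam rule stands uncontradicted. What remains is that the discontinuation section itself couples stopping treatment with stopping assessments, and schedules no outcome afterwards.

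A reader might also infer that intent-to-treat is breached. It is not: a likelihood model on all randomized subjects is compatible with it. The gap is that post-stop outcomes are unobserved and rest on an assumption.

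Nor is bias from removal for worsening shown. The listed triggers include a 25% rise in PCL-5 or CAPS-5 and a CGI of 6 or more. PCL-5 and CGI are recorded at nearly every visit after screening, so removal driven by them may be close to missing at random.

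Two safeguards exist. The SAP's responder analysis counts a missing subject as a failure for the assigned arm, although on a binary outcome. Pattern-mixture models are available, but conditionally, and a few stops may not look disproportionate. Both are partial.

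The illustration is also unfavourable by construction: all stops come at infusion 1 and in one arm. Later stoppers contribute several PCL-5 scores. The pilot reported that dissociative symptoms resolved within 80 minutes of ketamine administration, so persistence at the two-hour check should be uncommon. Lastly, stoppers may move to standard treatment, so their later scores would partly reflect other therapy. That affects interpretation, but such scores still belong to the effect of assignment.

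**Conclusion.** The concern holds in a limited form. Parts of the Protocol end participation where stopping infusions would do, no PCL-5 or CAPS-5 is scheduled after such a stop, and the sections disagree about when removal applies. For tolerability removals the likely direction is a slight overstatement of the 0.5 mg/kg effect of assignment.

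For 1 to 3 stops in 66 with no benefit kept, the overstatement of d = 0.80 is about 1.5% to 5%; with half the benefit kept, about 0.8% to 2.3%. This rests on assumed stop counts, removal at infusion 1 in one arm only, and assumed loss of benefit, none of which the documents supply. A shift of this size would be hard to see against sampling error, and nothing here suggests that it would reverse the trial's conclusion. The case for acting is that the correction costs little and removes an ambiguity between sites.

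**What to change.** **If assessments can still be collected.** In the Criteria for Discontinuation and the three safety-summary bullets, replace removal from the study with *discontinued from infusions*, and align them with the Infusion session 1 text and the ketamine safety paragraph. Unless consent is withdrawn or the clinician judges assessment unsafe, continue PCL-5 on the Table 2 days and CAPS-5 at Days 25 and 56. PCL-5 may be taken by phone if needed, as the Protocol already allows on Day 1. Include these scores in the intent-to-treat mixed model. Infusions still stop, so no safety protection is weakened.

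**If data collection is over**, as the SAP's past tense suggests it may be, run one return-to-placebo sensitivity analysis on PCL-5. Missing end-points in the ketamine arms are imputed from the placebo course, given the scores observed before the stop. Run it whether or not dropout looks imbalanced. It needs no new data.

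**Cost.** Protocol wording, a 20-item self-report on the remaining visit days, and up to two CAPS-5 interviews of about one hour by existing raters for each early stopper who agrees. Some of the later scores may reflect other treatment, so record that treatment alongside them.
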